3.1 Background Information

The goal of this study will be to continue development and commercialization of a new noninvasive transdermal alcohol monitor developed by KWJ Engineering, Inc. The wrist-mounted transdermal ethanol measurement system being studied in this proposal is part of the modern trend toward wearable and noninvasive measurements. In recent years there has been a growing trend in science and technology toward developing noninvasive on-body, continuous measurements in the management of chronic disease, monitoring the elderly, diagnostic sensing and other biomedical applications [1-7]. Stretchable and flexible materials for dermal sensors are emerging, as are new approaches to making physical and chemical measurements noninvasively on the skin [8-11]. KWJ engineering is an industry-leading manufacturer of monitoring sensors, instruments, and gas sensors designed to reduce risks to health, safety, and security in commercial and consumer environments. KWJ has recently received an SBIR phase II award from NIAAA to continue efforts to develop a wearable transdermal sensor that monitors Blood Alcohol Level (BAL) in real-time. The monitor is based on the KWJ Engineering's printed electrochemical gas sensor that is able to detect ethanol concentrations in the skin. This ethanol sensor is a very small, ultralow power, and highly sensitive device with very low interferences. In previous studies leading up to the SBIR award, KWJ Engineering has demonstrated stable and sensitive measurement of ethanol across human skin surrogate membranes. This was accomplished with an initial prototype wristwatch device that included the ethanol sensor and circuitry for performing the measurement and converting data for wireless communication to a computer. Raw transdermal ethanol concentrations were calibrated to blood alcohol values using standardized ethanol solutions as a surrogate for blood alcohol concentration (BAC). KWJ has demonstrated a high degree of reproducibility in measurement sensitivity across several watch format devices.

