4.1 Study Objectives

The specific objective of this study is to determine whether the printed electrochemical gas sensor designed to measure BAL will be sensitive and reliable when compared to a standard measure of BAL taken by a breathalyzer (Intoximeter Alco-Sensor IV). If this sensor proves sensitive to changes in BAL and can reliably measure BAL relative to a “gold standard” method, there are significant opportunities to use this technology in consumer health applications and clinical research.

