Predicted BAL that will be determined from TAC data are expected to be equivalent to BrAc concentrations. We, therefore hypothesize that there will be a strong correlation between BAL and BrAc measurements obtained at the same time points for the individual subjects. The reference breathalyzer response is known to be linear over the range of expected blood alcohol levels in the study [23]. Therefore, the breathalyzer and predicted BAL values are expected to be linearly related to each other. To confirm the hypothesis that these values are highly linearly related an analysis will be conducted in which repeated measures correlation coefficient (rcmm) between BrAc and BAL will be obtained. In contrast to a simple correlation analysis of data in which repeated measures collected from individual subjects are used, here will be no violation of the assumption of independence of observations when rcmm values are utilized as the measure of the extent of correlation between these values [Bakdash and Marrusich, 2017].

Calibration Study of a Wearable Noninvasive Blood Alcohol Monitor
Final V1.8 4.24.19

Data obtained in the validation phase of this study will be analyzed using the proc glm procedure for SAS 9.4. This data will include values for individual subjects obtained for each time-point at which BrAc measurement were made and corresponding predicted BAL values determined for these subjects. This data will be analyzed using following general linear model:

BAL= BrAc sub

This model is equivalent to an analysis of covariance model in which subjects (sub) are a covariate. This model will allow for the determination of whether BrAc and BAL values are significantly related to one another. The correlation coefficient [rcmm] for relationship between BAL and BrAc will be determined using the following equation first mentioned by Bland and Altman [24] with sum of squares values being obtained from the results of our glm analysis: $rcmm = \text{square root} [\text{Sum of Squares BAL} / (\text{Sum of Squares BAL} + \text{Sum of Squares Residual})]$

Since both BrAc and BAL measurements are hypothesized to be linear, the rcmm value is expected to be >0.80 with high correlation power. The statistical null hypothesis is that the predicted BAL measurements are not related to the standard breathalyzer measurements. The study is designed to maintain a probability of Type I and Type II error rates with respect to the null hypothesis at $p<0.05$.

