Given that BAL and BrAc are expected to be equivalent it is also hypothesized that there will be a strong correlation between Cmax and Tmax values. Pearson correlation coefficients for correlation analysis between both Cmax and Tmax determined from individual subjects' BrAc and BAL curves, therefore, are expected to be 0.8 or greater, with p values being less than 0.05.

Hypothesis	Planned Analyses
1. There will be a significant correlation between BrAc predicted BAL measures	Repeated measures correlation analysis of wristwatch TAC measurements and contemporaneous BAC measurements from breathalyzer.
2. There will be a significant correlation between Cmax and Tmax values obtained for paired BrAc and predicted BAL measurements.	Pearson correlation analysis for Tmax and Cmax values obtained for BrAc and predicted BAL data.

We expect that the results of this study will demonstrate the effectiveness of the developmental wristwatch transdermal alcohol sensor. Furthermore, these results and the developmental work to calibrate this wristwatch will contribute significant knowledge toward the understanding of reliable measurement of blood alcohol via transdermal routes.

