12.2 Sample Size Determination

Calibration Study of a Wearable Noninvasive Blood Alcohol Monitor

Final V1.8 4.24.19

Power analysis: Eight concurrent readings of breathe (BAL) and transdermal alcohol concentration (TAC) will be obtained from the wristwatch sensor and the breathalyzer starting 15 minutes after the start of subject alcohol consumption to the end of the 60 minute drinking session. An additional 20 concurrent readings will be collected during the 5 hour observation period in phase I, and an additional 12 concurrent readings in the 3-hour observation period in phase II. This means that a possible 28 (Phase I) or 20 (phase II) points may be available for this analysis if only pairs of data are used for which values for both devices exceed zero. However, the sensitivity of the wristwatch sensor in human subjects is currently unknown, and so fewer than 20 data points may be of use for our analysis.

Data will be analyzed using a repeated measures correlation (rcmm) procedure described by Bland and Altman [24] and Bakdash and Marisich [25]. For the wristwatch device to be considered to be useful the r value for the correction between BrAc and predicted BAL measures must exceed 0.9. Cohen [26] defines a large effect size as being $r=0.5$. Bakdash and Marish provide power curves for the rcmm procedure. These curves indicate that for a large effect size ($r=0.5$) that the power approach 99% when data from only 10 points are available for sample size of about 7. We anticipate a repeated measures correlation value of at least 0.8 and hope to observe a correlation of 0.9. Bakdash and Marisich [25] indicate the degrees of freedom for determining rcm values can be determined using the following equation:

$$Df = (\text{Number of subjects}-2) \times (\text{number of data points} - 1).$$

The degrees of freedom can be used to determine the corresponding sample size, with the degrees of freedom for standard tables of power analysis being equal to $N-2$ ($Df=N-2$). Using this relationship we use the Proc Power procedure for Pearson correlations in SAS to determine the power for 21 data points collected for 9 subjects and 10 datapoints for 5 subjects. In both of these analyses the calculated power value was > 0.995 for rcm of 0.8 or 0.9.

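### Session two is meant to test the watch's accuracy, but every formal analysis is a correlation, which cannot show a scale or level error in predicted BAL

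*Combined protocol and SAP*

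**What the plan says.** The synopsis (Design/Methodology) makes accuracy against breath testing the end goal and describes the second self-administration session as the test of it. Section 4.1 words the specific objective differently, asking "whether the printed electrochemical gas sensor designed to measure BAL will be sensitive and reliable when compared to a standard measure". Section 4.2.1 makes the primary outcome a repeated measures correlation in session two.

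Section 12.1 (Validation Phase) starts from equivalence, "Predicted BAL that will be determined from TAC data are expected to be equivalent to BrAc concentrations", and infers that a strong correlation should follow. The hypothesis tested is: "The statistical null hypothesis is that the predicted BAL measurements are not related to the standard breathalyzer measurements". The secondary analyses follow the same pattern: "it is also hypothesized that there will be a strong correlation between Cmax and Tmax values", assessed by Pearson coefficients. Section 12.2 falls back on Pearson correlations of AUC and Cmax if a time lag makes the repeated measures coefficient unusable. The one numeric condition for usefulness is also there: for the device to be "considered to be useful the r value for the correction between BrAc and predicted BAL measures must exceed 0.9".

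Two planned items do touch on level. Section 12.1 has each subject's BrAC and predicted BAL curves examined for systematic Cmax and Tmax differences, and the PROC GLM model (predicted BAL on BrAC and subject) yields a BrAC slope.

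**The concern.** Equivalence implies correlation, but correlation does not imply equivalence. Rejecting a null of no relation shows association only, and r > 0.9 shows close linear tracking only. A watch could track breath alcohol well, meet every numeric target in the plan, and still be wrong in level by an amount that nobody estimates.

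The question is a live one here. Section 9 applies the Phase I model to second generation sensors in Phase II, and Section 12.2 says that "the sensitivity of the wristwatch sensor in human subjects is currently unknown". A shift in scale between phases is therefore possible, though the documents give no size for one. At stake is whether the accuracy question in the synopsis gets a quantified answer or rests on unstructured inspection of about nine pairs of curves.

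**Working it through.** **The plan's own power figures reproduce.** Pearson r = 0.8, n = 9, two-sided alpha 0.05: simulation of the t-test gives 0.819, against the stated 0.82. For the repeated measures coefficient, the plan's df formula gives (9 − 2)(21 − 1) = 140 and (5 − 2)(10 − 1) = 27. Fisher's z with N = df + 2 gives power above 0.9998 at r = 0.8 in both cases, against the stated > 0.995. The issue is what the tests measure, not their power.

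**Invariance (no assumptions needed).** The coefficient is r = √[SS_BrAC / (SS_BrAC + SS_residual)] from predicted BAL = BrAC + subject. (The plan labels the first term BAL; I take it as the BrAC term, since BAL is the dependent variable.)
- Multiply predicted BAL by g > 0: both sums of squares are multiplied by g², so r is unchanged.
- Add a constant for each subject: the subject term absorbs it, so r is unchanged.
- Pearson r for Cmax or AUC is likewise unchanged by a common gain and a common offset.

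Numerical check on one simulated data set, with predicted BAL × 1, × 0.8, × 1.2, × 0.5, and × 0.8 plus 0.010 g/dL: r = 0.9517 every time. The slope was 0.97, 0.78, 1.17, 0.49 and 0.78.

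**Size of a 20% error.** Target peak 0.05 g/dL (Section 5). I assume a linear rise over 1 h, a fall of 0.015 g/dL/h, and readings every 15 min for 4 h, which is 16 readings.
- At peak: 0.2 × 0.05 = 0.010 g/dL.
- Mean BrAC: (0.125 over the first 4 readings + 0.3075 over the next 12) / 16 = 0.0270, so session-mean bias = 0.2 × 0.0270 = 0.0054 g/dL.

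**Expected r (error SDs are assumptions; the documents give none).** The within-subject sum of squares of BrAC is 0.002887, so the variance is 0.002887 / 15 = 0.0001925 and S = 0.01387. If error does not scale with gain, r ≈ gS / √(g²S² + SD²). At SD 0.005:
- g = 0.8: 0.01110 / 0.01217 = 0.91
- g = 1.0: 0.01387 / 0.01475 = 0.94
- g = 1.2: 0.01665 / 0.01738 = 0.96

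If error scales with gain, g cancels and r = 0.94 at every g.

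**Share of simulated trials with r > 0.9** (9 subjects; peak SD 0.0075, subject offset SD 0.003; approximate):

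| Error model | Readings used | 20% low | Correct | 20% high |
|---|---|---|---|---|
| Unscaled, SD 0.005 | all 16 | 85% | 100% | 100% |
| Unscaled, SD 0.005 | watch readings below 0 / 0.010 / 0.015 dropped | 68 / 16 / 2% | not needed here | over 99% |
| Unscaled, SD 0.005 | first 10 only | 11% | not needed here | over 99% |
| Scaled, SD 0.005 | all 16 | 100% | 100% | 100% |
| Unscaled, SD 0.0075 | all 16 | not needed here | 9% | 85% |
| Scaled, SD 0.0075 | all 16 | 7–9% | 7–9% | 7–9% |

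A second set of assumed curves gave 69% (16 readings) and 74% (20 readings) for the low-reading watch at unscaled SD 0.005, and 3–5% at SD 0.006. Lost low readings matter because Section 12.2 contemplates using only pairs in which both devices exceed zero.

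**Raw Cmax is a poor measure of level error.** The maximum of noisy readings is biased upward, and using the same rule on both devices does not cancel unequal noise. With breathalyzer SD 0.002, a correct watch shows a Cmax difference of +0.0015 / +0.0037 g/dL at watch SD 0.005 / 0.0075. At watch SD 0.0075, a true −0.010 peak error appears as about −0.005.

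**The case against.** The best defence is that this is a small development study whose specific objective concerns sensitivity and reliability, with a primary outcome openly stated as a correlation. Correlation suits sensitivity to change. The Phase I model is largely a lag correction, and the repeated measures coefficient does respond to how well lag is removed. Curve inspection would probably reveal a gross error such as a doubled peak. Section 3.1 adds that "KWJ has demonstrated a high degree of reproducibility in measurement sensitivity across several watch format devices". All of this stands in part. But the reproducibility was shown in work on skin surrogates. The inspection has no statistic, margin or link to the usefulness condition. From the GLM the plan takes only significance and sums of squares, not the slope. The zero-BAL hour checks only zero.

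A reader might go further than the documents allow in four ways:
- *Any mis-scaled watch will pass r > 0.9.* Not so. With unscaled error a low-reading watch often fails, above all when low or late readings are lost.
- *The criterion favours an over-reading watch over a correct one.* That contrast (85% against 9% at SD 0.0075) needs unscaled error and vanishes if error scales with gain. The documents support neither model.
- *The primary analysis will use unconverted sensor data.* The table in Section 12.1 does describe "Repeated measures correlation analysis of wristwatch TAC measurements and contemporaneous BAC measurements from breathalyzer", but its hypothesis column and the text specify predicted BAL. This is probably loose wording that needs aligning.
- *The watch is in fact mis-scaled.* Nothing in the documents shows this.

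**Conclusion.** The point holds and should be fixed before Phase II. No planned formal analysis can show a scale or level error in predicted BAL, so the accuracy question has no quantified answer. That part is algebra and rests on no assumption.

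The practical size does depend on assumptions about curve shape, error SD and error model. Under them, r > 0.9 can miss a 20% over-reading (0.010 g/dL at peak, about 0.0054 in session mean) in nearly every trial at SD 0.005. It misses a 20% under-reading only in some settings: about 2% to 85% of trials with unscaled error, depending on which readings are usable, and all trials if error scales with gain. The correlation remains valid as a measure of tracking.

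**What to change.** Keep the repeated measures correlation as the measure of tracking, and state that r > 0.9 is necessary but not sufficient for accuracy. Align the Section 12.1 table with the text on TAC versus predicted BAL. Before Phase II, prespecify:

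1. **Mean bias** (predicted BAL − BrAC) with a 95% CI from one mean difference per subject (t, n − 1 df), judged against a margin the sponsor fixes in advance.
2. **95% limits of agreement** allowing for repeated measures, and **RMSE**.
3. **Level error near peak**, as the mean paired difference at time points fixed in advance or chosen from BrAC timing, or from curves smoothed by a prespecified method. Do not use each device's raw maximum. This is needed beside mean bias because a proportional error gives a mean bias only 0.0270 / 0.05 = 0.54 of its size at peak.
4. **Descriptive only:** raw Cmax and Tmax differences with CIs, and calibration slope and intercept from subject-level or random slopes. Breathalyzer error and residual lag pull the slope below 1, so a slope of 1 should not be a pass/fail test.

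Base the agreement statistics on all planned pairs, not only those where both devices exceed zero.

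The cost is a little analysis work and commitment to a margin; no visits or readings are added. Precision is limited: with 9 subjects the half-width for mean bias is t(0.975, 8)/√9 = 0.77 × the SD of subject mean differences, or 0.0023 / 0.0038 / 0.0077 g/dL at assumed SDs of 0.003 / 0.005 / 0.010. Power to detect a 0.0054 bias is then >99 / 81 / 30%. If subjects vary widely, only a large bias can be excluded, and the interval will show that.

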4.2 Study Outcome Measures

4.2.1 Primary Outcome Measures

The primary outcome is the correlation in estimated BAL as measured by the breathalyzer and the wristwatch sensor during the second alcohol self-administration trial. BAL and wristwatch sensor data correlation will be analyzed by repeated measures correlation (rmcorr) analysis, as described in more detail in section 12.

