If the existence of a time lag is found that precludes the usefulness of rcm values then Pearson correlations will be determined for AUC and Cmax values. For both of these value obtained for the TAC-BAL data for $r=0.8$, power will equal 0.82 for a sample size of 9 subjects who complete Phase I and Phase II. We anticipate consenting 36 subjects to achieve a sample size 12 randomizers and 9 completers.

Given that this is a laboratory-based experiment we do not plan to conduct any planned interim analyses in this study.

13 Ethics/Protection of Human Subjects

This study is to be conducted according to applicable US federal regulations and institutional policies (which are based in federal regulations, guidance, and ICH Good Clinical Practice guidelines).

This protocol and any amendments will be submitted to the Boston Medical Center and Boston University Medical Campus IRB, for formal approval of the study conduct. The decision of the

Calibration Study of a Wearable Noninvasive Blood Alcohol Monitor

Final V1.8 4.24.19

IRB concerning the conduct of the study will be made in writing to the investigator. A copy of the initial IRB approval letter will be provided to the sponsor before commencement of this study.

All subjects for this study will be provided a consent form describing this study and providing sufficient information for subjects to make an informed decision about their participation in this study. The consent form will be submitted with the protocol for review and approval by the IRB. The consent of a subject, using the IRB-approved consent form, must be obtained before that subject is submitted to any study procedure. Consent will be documented as required by the IRB.

14 References

1. Pantelopoulos, A. and N.G. Bourbakis, A survey on wearable sensor-based systems for health monitoring and prognosis. *IEEE Transactions on Systems, Man and Cybernetics, Part C (Applications and Reviews)*, 2010. 40(1): p. 1-12.
2. Allet, L., et al., Wearable Systems for Monitoring Mobility-Related Activities in Chronic Disease: A Systematic Review. *Sensors*, 2010. 10(10): p. 9026-9052.
3. Patel, S., et al., A review of wearable sensors and systems with application in rehabilitation. *Journal of Neuroengineering and Rehabilitation*, 2012. 9: p. 17.
4. Y. Hao, R. Foster, "Wireless Body Sensor Networks for Health Monitoring Applications," *Physiol. Meas.*, 29, R27-R56 (2008).

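### The primary rcmm equation has no sign, and no rule in the plan requires a positive BrAc slope, so an inverse relation would be reported as a positive correlation

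*Combined protocol and SAP*

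**What the plan says.** Section 4.2.1 makes the primary outcome the correlation between breathalyzer and wristwatch BAL in the second session: "BAL and wristwatch sensor data correlation will be analyzed by repeated measures correlation (rmcorr) analysis".

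Section 12.1 (Validation Phase) fits a general linear model in PROC GLM with predicted BAL as the response and BrAc and subject as terms. It then introduces a hand calculation: "The correlation coefficient [rcmm] for relationship between BAL and BrAc will be determined using the following equation". The equation is the square root of SS / (SS + residual SS), "with sum of squares values being obtained from the results of our glm analysis". No sign is attached to the root.

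Three statements say what the coefficient is used for:

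- Section 12.1, expectation: "the rcmm value is expected to be >0.80 with high correlation power".
- Section 12.1, hypothesis 1 in the table: "There will be a significant correlation between BrAc predicted BAL measures".
- Section 12.2, usefulness of the device: "the r value for the correction between BrAc and predicted BAL measures must exceed 0.9".

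The statistical null in Section 12.1 is absence of a relation, with no direction. Sidedness of the test is not stated. Nowhere do the documents say that rcmm takes the sign of the BrAc slope, or that the slope must be positive.

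**The concern.** A correlation meant to show that the watch follows breath alcohol should separate moving together from moving apart. This one cannot. Using the correct sum of squares does not help. The equation labels its term as BAL, which is the response, whereas the model supplies a term for BrAc; that is a separate matter, and the root is unsigned either way. The GLM F test of the BrAc term also ignores direction.

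Direction is not an idle question in this study. Section 12.1 expects TAC to peak later than BrAc in most subjects. If part of that delay remains in the tested series, breath alcohol is already falling while the watch value is still rising, and the within-subject correlation can turn negative. The written equation would drop the minus sign, and beyond some lag the reported value would improve as tracking worsens. Hypothesis 1 and the 0.9 rule both rest on this statistic.

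**Working it through.** **1. The plan's power figure.** Section 12.2 uses df = (subjects - 2) x (points - 1) and N = df + 2.

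- 9 subjects x 21 points: df = 7 x 20 = 140, N = 142; power about 1.000 at r = 0.8 and 0.9.
- 5 subjects x 10 points: df = 3 x 9 = 27, N = 29. By Fisher's z at r = 0.8, two-sided 0.05: 1.0986 x sqrt(26) - 1.96 = 3.64, so power is 0.9999.

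Both agree with the stated value above 0.995. A sign rule does not alter this for a watch that moves with breath alcohol.

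**2. Range of the equation.** SS and residual SS are both non-negative, so SS / (SS + residual SS) lies in [0, 1], and so does its square root. The signed version is sign(BrAc coefficient) x the same root.

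**3. Inverted watch (simulation).** 9 subjects x 20 points (the Phase II count in Section 12.2), true slope -1, residual df 170. The noise SDs are assumptions.

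| Noise SD (g/dL) | Written equation | Signed |
|---|---|---|
| 0.002 | +0.988 | -0.988 |
| 0.004 | +0.956 | -0.956 |
| 0.006 | +0.908 | -0.908 |
| 0.010 | +0.794 | -0.794 |

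Three of these four exceed 0.9 as written; none does with the sign.

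**4. Residual lag (more plausible than outright inversion).** From the documents: target peak 0.05 g/dL after a one-hour drinking session, readings every 15 minutes, three hours of Phase II observation. That gives 4 + 12 = 16 readings; Section 12.2 counts 20, and spreading 20 points over the same window changes little (-0.52 and -0.73 at 1.5 and 2 h). Assumed: linear rise to the peak at 1 h, fall of 0.015 g/dL per hour, a noise-free watch equal to the breath curve shifted by the lag, and the same curve for every subject, so that the within-subject r equals the single-curve r.

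| Lag left in tested series | Signed r, all 16 pairs | Written equation |
|---|---|---|
| 0.5 h | +0.58 | 0.58 |
| 1 h | -0.08 | 0.08 |
| 1.5 h | -0.50 | 0.50 |
| 2 h | -0.71 | 0.71 |
| 2.5 h | -0.77 | 0.77 |

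At 2 h the signed value is -0.61 to -0.77 for falls of 0.012 to 0.018 g/dL per hour.

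**5. Significance.** For 9 x 16 pairs, residual df = 9 x 15 - 1 = 134. Critical t is 1.978, so critical |r| = 1.978 / sqrt(134 + 1.978²) = 0.168. The 1.5 to 2.5 h values are well beyond this in size.

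**6. Can a lag alone reach 0.9?** With all 16 pairs, lags up to 2.5 h, smoothing time constants up to 1 h and falls of 0.012 to 0.018, the largest size was 0.85. At a 2 h lag and a fall of 0.015:

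| Smoothing 0.5 h | Only pairs above zero on both devices | Signed r |
|---|---|---|
| no | no | -0.71 |
| yes | no | -0.79 |
| no | yes (8 pairs) | -0.57 |
| yes | yes (8 pairs) | -0.94 |

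Without smoothing, the above-zero restriction takes the size past 0.9 only at longer lags, for example -1.00 at 3 h on 4 pairs per subject.

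**The case against.** The best counter-argument is that direction is implied and that a reversal would be noticed. Section 12.1 expects predicted BAL to be equivalent to BrAc, which makes sense only for a positive relation. The tested series is predicted BAL, from a Phase I model built to remove the lag, so a residual lag of 1.5 to 2 h means that model has failed. Section 12.1 also plans BrAc and predicted-BAL curves for each subject, examined for systematic Tmax differences, and Section 12.2 has a fallback to AUC and Cmax correlations: "If the existence of a time lag is found that precludes the usefulness of rcm values". The fitted model yields the slope itself. Finally, Sections 4.2.1 and 12.2 rely on published repeated measures correlation methods, which may carry a sign convention.

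Much of this stands, and it lowers the practical risk. It does not close the gap. The expectation of equivalence is not written into the null, the hypothesis table or the 0.9 rule. The curve review has no decision rule, and the fallback has no numeric trigger. The Pearson tests on Cmax and Tmax are signed, but a lag common to all subjects need not lower them. The cited methods are not reproduced, whereas Section 12.1 writes out its own equation, which is what a programmer would follow.

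A reader might go further and infer that a lagging watch is likely to pass the 0.9 rule. The documents do not support that. The 0.94 case needs an uncorrected 2 h lag, added smoothing and the above-zero restriction together, and Section 12.2 mentions that restriction only conditionally. Nor does the five-hour Phase I observation imply a lag of that order: it is a window chosen to be sure of capturing the TAC peak, and the documents give no lag figure.

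**Conclusion.** The defect holds as a property of the written primary formula: it cannot be negative, and nothing in the plan ties significance or usefulness to a positive slope. An inverse within-subject relation would therefore be reported as a positive correlation and would count as significant once its size passed the critical value.

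Its illustrative size is a sign reversal from about -0.50 to -0.71 into +0.50 to +0.71 at 1.5 to 2 h of residual lag, with all pairs staying at or below about 0.85. Exceeding 0.9 needs near-inversion, or a long residual lag, usually with smoothing, plus the above-zero restriction. The lags, smoothing, noise and rate of fall are all assumptions. Given the Phase I lag model, the curve review and the fallback, severity is moderate to minor: worth correcting because the primary statistic is affected, but not evidence that the study would reach a wrong conclusion.

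**What to change.** Add to Section 12.1, directly after the equation: rcmm takes the sign of the fitted BrAc coefficient in the model, and hypothesis 1 and the r > 0.9 criterion are met only if that coefficient is positive. Repeat the condition beside the 0.9 rule in Section 12.2.

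The cost is one sentence of text and one line of SAS code. It needs no further data or subjects, and it leaves both the result and the stated power unchanged for a watch that moves with breath alcohol.
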